2 STATISTICAL AND ANALYTICAL PROCEDURES

2.1 ANALYSIS ENDPOINTS

2.1.1 Demographic and baseline characteristics

Demographic characteristics

Demographic variables include:

- Age in years
 - Continuous
 - Categorical (age <18, 18≤ age <65, 65≤ age <75, 75≤ age < 85, age ≥85 years)
- Sex (Male, Female)
- Weight in kilograms
 - Continuous
 - Categorical (<50, ≥50-<100, ≥100)
- BMI in kg/m²
 - Continuous
 - Categorical (<18.5, ≥18.5-<25, ≥25-<30, ≥30)
- Subject enrollment status after ending parent study (within 4 weeks, more than 4 weeks)
- Alcohol Habits
 - How often subject has a drink containing alcohol in the last 12 months? (Never, At least monthly, At least weekly, At least daily)
 - How many standard drinks containing alcohol subject has on a typical day when drinking? (1 or 2, Greater than 2)
- Smoking History
 - Smoking Status (Never, Former)
 - Average Consumption (pack per day) – continuous
 - Number of Years Smoked (years) – continuous
- Pregnancy Test
 - Performed (Yes, No)
 - Results (Positive, Negative)

Medical history and disease characteristics at baseline

Relevant medical and surgical history is collected on corresponding CRF.

Statistical Analysis Plan
LPS15023 - Dupilumab

15-Mar-2021
Version number: 2.0

2.1.2 Prior or concomitant medications

All medications will be coded using the World Health Organization-Drug Dictionary (WHO-DD) using the version currently in effect at Sanofi at the time of database lock.

A concomitant medication is any treatment received by the patient concomitantly to the IMP.

Details related to computation, dates, imputation for missing dates are described in [Section 2.5](#).

2.1.3 Efficacy endpoints

Not applicable

2.1.4 Safety endpoints

Primary endpoint:

- Incidence rates, defined as the percentage of patients reporting any treatment-emergent adverse events (TEAEs), and event rates defined as number of TEAEs per 100 person-years.

Secondary endpoints:

- Incidence rates and event rates per 100 person-years for AESIs over the study.
- Incidence rates for SAEs/death over the study.
- Incidence rates for AEs leading to study discontinuation over the study.

2.1.4.1 Adverse events variables

AEs and SAEs are defined in Protocol [Section 10.4.1](#).

Adverse events reported in this study will be coded using the version of the Medical Dictionary for Regulatory Activities in effect at Sanofi at the time of database lock. Adverse events occurred during the treatment-emergent period will be considered as TEAE.

An AESI is an AE (serious or nonserious) of scientific and medical concern specific to the Sponsor's product or program, for which ongoing monitoring and immediate notification by the Investigator to the Sponsor is required. Such events may require further investigation in order to characterize and understand them; AESIs may be added, modified or removed during a study by protocol amendment.

The following is a list of AESIs for this study. For these AESIs, the Sponsor will be informed immediately (i.e. within 24 hours), per SAE notification described in Protocol [Section 10.4.1.2](#), even if not fulfilling a seriousness criterion, using the corresponding screens of the eCRF:

- Anaphylactic reactions or acute allergic reactions that require immediate treatment (see Protocol [Appendix F](#)).
- Injection site reactions that are severe and last longer than 24 hours.

Statistical Analysis Plan
LPS15023 - Dupilumab

15-Mar-2021
Version number: 2.0

- Any serious infection, any bacterial infection requiring treatment with parenteral antibiotics for longer than 2 weeks, any parasitic infection, any systemic opportunistic infection (see Protocol [Appendix E](#)), any viral infection requiring antiviral treatment, or any uncommon, atypical, or unusually frequent or persistent infection and TB that requires anti-TB medication. For details, refer to Protocol [Section 10.6.3](#).

Note: Candidiasis – all cases should be collected as AEs (or SAEs if requirements met), however, only cases which are NOT cutaneous (systemic or mucous membranes involved) unless involvement is extensive, will be considered as AESI.

- Pregnancy (female patient or female partner):
 - Pregnancy occurring in a female patient entered in the clinical trial or in a female partner of a male patient entered in the clinical trial. It will be qualified as an SAE only if it fulfills one of the seriousness criteria (see Protocol [Section 10.4.1.2](#)).
 - In the event of pregnancy in a female participant, IMP should be permanently discontinued.
 - Follow-up of the pregnancy in a female participant or in a female partner of a male participant is mandatory until the outcome has been determined.
- Symptomatic overdose (serious or nonserious) with the IMP/NIMP.
 - An overdose (accidental or intentional) with the IMP/NIMP is an event suspected by the Investigator or spontaneously notified by the patient and defined as at least twice the planned dose during an interval of less than 11 days. The circumstances (i.e. accidental or intentional) should be clearly specified in the verbatim and symptoms, if any, entered on separate AE forms.
 - Of note, asymptomatic overdose has to be reported as a standard AE.

2.1.4.2 Deaths

Deaths will be collected from the time of informed consent signature and then at each visit until the EOT/EOS (Visit 13).

2.1.4.3 Laboratory safety variables

Clinical laboratory data will be limited to hematology (blood count: erythrocytes, hemoglobin, hematocrit, leukocytes with differential blood count [neutrophils, lymphocytes, monocytes, eosinophils, and basophils] and platelets), and pregnancy testing.

Only clinically significant laboratory test results will be recorded as AEs in the eCRF.

2.1.4.4 Vital signs variables

Symptom-driven physical examination and vital signs will be performed in patients presenting with signs or symptoms.

2.1.4.5 Electrocardiogram variables

Not applicable

Statistical Analysis Plan
LPS15023 - Dupilumab

15-Mar-2021
Version number: 2.0

2.2 DISPOSITION OF PATIENTS

Enrolled patients consist of all the patients who signed informed consent and had a treatment kit number allocated and recorded in IRT database, and regardless of whether the treatment kit was used or not.

The safety population consists of the patients who actually received at least one dose or part of a dose of dupilumab in the current study.

For patient study status, the total number of patients in each of the following categories will be presented in the clinical study report using a flowchart diagram or summary table:

- Enrolled patients
- Safety population: patients who received at least one dose in the current study
- Patients who did not complete the study treatment period as per protocol
- Patients who permanently discontinued study treatment by main reason
- Patients who did not complete study follow-up period as per protocol
- Patients who discontinued study by main reason

For all categories of patients, percentages will be calculated using the number of enrolled patients. Reasons for treatment and/or study discontinuations will be supplied in tables giving numbers and percentages.

All critical or major deviations potentially impacting analyses, enrollment, and drug-dispensing irregularities, and other major or critical deviations will be listed.

A patient is considered lost to follow-up at the end of the study if he/she is not assessed at the last protocol planned visit.

2.2.1 Randomization and drug dispensing irregularities

Not applicable

2.3 ANALYSIS POPULATIONS

The enrolled population includes all enrolled patients and will be used to summarize demographics and baseline characteristics.

2.3.1 Efficacy populations

Not applicable

2.3.2 Safety population

The primary analysis population is the safety population, defined as all patients who have received at least one dose or part of a dose of dupilumab during this study.

Statistical Analysis Plan
LPS15023 - Dupilumab

15-Mar-2021
Version number: 2.0

The treatment-emergent period is defined as the time from the first dose of dupilumab up to the last dose of dupilumab plus 2 weeks for completers, or plus 12 weeks for prematurely discontinued subjects.

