10.1.4 Visit 13 (End-of-treatment/End-of-study, Week 144)

This will be the end of treatment and the last study visit (except for patients who prematurely and/or permanently discontinue treatment, see [Section 10.1.5](#)).

The following procedures will be performed during this visit:

- Contact IRT to register the EOT/EOS Visit.
- Inquire for any AEs. In case of any such occurrences, AEs should be recorded and reported.
- Symptom-driven physical examination and vital signs should be performed in patients presenting with signs or symptoms.
- Collect the home-dosing diary and check for regular administration of study IMP/NIMP medication.
- Collect all used and unused IMP.
- Record study IMP/NIMP and all other concomitant medication use with start date/dose in the eCRF.

- Collect blood samples for hematology: Blood count (erythrocytes, hemoglobin, hematocrit, and leukocytes), differential blood count (neutrophils, lymphocytes, monocytes, eosinophils, and basophils), and platelets.
- For **WOCBP only**, blood or urine pregnancy test; WOCBP discontinuing treatment must be advised to avoid pregnancy for at least 12 weeks following the last IMP dose.
- Capture as AEs all clinically significant laboratory values in the eCRF.

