10.3.4 Handling of patients after permanent treatment discontinuation

If possible, and after the permanent discontinuation of treatment, patients will be assessed using the procedure normally planned for the last dosing day with the IMP (Visit 13). In case of an ongoing AE at the EOT/EOS Visit, patients may be followed up to recovery or stabilization of the AE.

All cases of permanent treatment discontinuation must be recorded by the Investigator in the appropriate screen(s) of the eCRF when considered as confirmed.

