11.3.2 Safety population

The primary analysis population is the safety population, which is defined as all patients who have actually received at least one dose or part of a dose of dupilumab during this study.

The treatment-emergent period is defined as the time from the first dose of dupilumab during this study up to the EOT/EOS (Visit 13).

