1.5 MODIFICATIONS TO THE STATISTICAL SECTION OF THE PROTOCOL

Not applicable

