2.4.5 Analyses of safety data

The primary and secondary analyses are safety related. All safety analysis will be performed on the safety population.

Statistical Analysis Plan
LPS15023 - Dupilumab

15-Mar-2021
Version number: 2.0

Treatment-emergent AE is defined as any AE with onset on or after the first dose of dupilumab up to the last dose of dupilumab plus 14 days for completers, or plus 84 days for prematurely discontinued subjects.

Primary endpoint:

- Incidence rates, defined as the percentage of patients reporting any treatment-emergent adverse events (TEAEs), and event rates, defined as the number of TEAE events per 100 person-years.

Secondary endpoints:

- Incidence rates and event rates per 100 person-years for AESIs over the study.
- Incidence rates for SAEs/death over the study.
- Incidence rates for AEs leading to study discontinuation over the study.

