2.4.5.6 Analyses of COVID-19-related variables

The number and percentage of patients with impact due to COVID-19 will be summarized using the number of patients with at least 1 impacted site visit, the number of patients with at least 1 visit with different impact type (visit not done, visit partially done, visit delayed), the number of visit types (vital signs, local laboratory hematology, pregnancy tests, physical examination and follow-up, investigational product administration, and contact form), and the number of patients impacted per visit. Wave 3 analyses will be performed by assessment and visit type, and stratified by country (France, Canada, and Israel). COVID-19-related analysis will also include Argentina and South Africa in the final analysis.

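### For completers the SAP ends the treatment-emergent window at last dose + 14 days where the protocol ends it at Visit 13; the undeclared change leaves some collected AEs uncounted

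*SAP*

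**What the plan says.** - **Window, protocol.** Protocol 11.3.2 defines the treatment-emergent period as the time "from the first dose of dupilumab during this study up to the EOT/EOS (Visit 13").
- **Window, SAP.** SAP 2.3.2 runs it "up to the last dose of dupilumab plus 2 weeks for completers, or plus 12 weeks for prematurely discontinued subjects". SAP 2.4.5 repeats this in days (14 and 84) and ties it to onset: a TEAE is "any AE with onset on or after the first dose of dupilumab up to the last dose of dupilumab plus 14 days for completers".
- **Role.** Both documents make an AE a TEAE if it falls in this period (Protocol 11.4.3.1, SAP 2.1.4.1), so the window decides what enters the primary endpoint.
- **Declaration.** SAP 1.5, headed "MODIFICATIONS TO THE STATISTICAL SECTION OF THE PROTOCOL", is marked not applicable. SAP 1.6 records only the added COVID-19 section.
- **Collection.** Protocol 9.2 collects AEs until Visit 13. Protocol 10.1.4 schedules an AE inquiry, hematology and a pregnancy test at that visit, with the instruction "Capture as AEs all clinically significant laboratory values in the eCRF".
- **Dosing at Visit 13.** The flow chart and Protocol 10.1.4 show none. Protocol 10.3.4, however, has patients assessed "using the procedure normally planned for the last dosing day with the IMP (Visit 13").
- **Person-time.** SAP 2.4.5.1 uses (last dose − first dose + 14 days)/365.25. The same paragraph says that all events reported in the follow-up period are counted, then puts only TEAEs in the formula.

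**The concern.** The two documents define the primary endpoint's window differently, and a reader of SAP 1.5 would assume that the protocol window still applies. On the nominal schedule the SAP window has no slack: it closes on the day of Visit 13. Several ordinary events then push part of the follow-up outside it: a late visit, a last dose given early within the 14±3-day interval, or a missed last home dose. The SAP itself expects disturbed visits. Section 2.4.5.6 tabulates "visit not done, visit partially done, visit delayed", although it does not single out Visit 13.

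At stake are AEs that sites must record but that the SAP would class as posttreatment. The clearest case is a laboratory abnormality, or a pregnancy, dated to the test done at a Visit 13 held after last dose + 14 days. Against the protocol window the SAP rule in practice only removes such events, because AE collection for completers ends at Visit 13. A few missing events matter most for rare adverse events of special interest (AESIs).

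**Working it through.** **1. Where the window closes.** Visits are 12 weeks apart with 12 after baseline (protocol synopsis), so Visit 13 is at 12 × 12 = Week 144 = Day 1008. Dosing every 2 weeks from Week 0 with none at Visit 13 gives 72 dosing days, the last at Week 142 = Day 994. The SAP window closes on Day 994 + 14 = Day 1008. If a dose were given at Visit 13, as Protocol 10.3.4 could imply, it would close on Day 1008 + 14 = Day 1022 and the gap would vanish.

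**2. When a gap opens.** Gap = max(0, Visit 13 day − (last dose day + 14)).

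| Visit 13 | Last dose | Gap (days) |
|---|---|---|
| on time | Day 994 | 0 |
| on time | 3 days early | 3 |
| on time | Week 142 dose missed (last dose Day 980) | 14 |
| 3 days late | 3 days late | 0 |
| 7 days late | Day 994 | 7 |
| 7 days late | 3 days early | 10 |

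The 7 days is an assumption. The ±7-day footnote in the flow chart is attached to Visits 2 to 12, and no window is stated for Visit 13.

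**3. How often.** Take the Visit 13 offset as uniform on −7 to 7 days and the last-dose offset D as uniform on −3 to 3, independent of it. The share of completers with any gap is the mean of (7 − D)/15 = 7/15 = 47%. This is the share with a gap of at least one day, not the share of events lost.

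**4. Size for all AEs (constant rate assumed).**
- Share of the window: 7/1015 = 0.7%; for 10 days, 10/1018 = 1.0%.
- Share of the time since Visit 12 (nominal Day 924): 7/91 = 7.7%, so about 92% of AEs arising since Visit 12 still count.
- Upper bound on events, if all 750 expected patients completed with a 7-day gap: 750 × 7/365.25 = 14.4 person-years. That is about 7 TEAEs at 50, and 43 at 300, per 100 person-years. The documents give no rates, so these are assumed.

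**5. Size for the percentage with any TEAE.** Only a first TEAE falling in the gap changes it: exp(−rT) × (1 − exp(−rg)), with T = 1008/365.25 = 2.76 years and g = 7/365.25 = 0.0192 years.
- r = 0.5 per year: 0.252 × 0.00954 = 0.24 points
- r = 1: 0.12 points
- r = 2: 0.015 points

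A 10-day gap at r = 0.5 gives 0.34 points. A missed Week 142 dose with Visit 13 on time closes the window on Day 994 and leaves 14 days: exp(−0.5 × 994/365.25) × (1 − exp(−0.5 × 14/365.25)) = 0.256 × 0.0190 = 0.49 points.

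**6. Size for AEs dated to a scheduled test.** These cluster on visit days, so the constant rate does not describe them. Visit 13 is 1 of 12 scheduled post-baseline draws. Under the assumptions of step 3, with equal yield per draw and onset dated to the sample, 0.467/12 = 3.9% of such AEs in completers would be left out.

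**7. Event rate.** For completers the event window (SAP 2.4.5) and the person-time (SAP 2.4.5.1) both end at last dose + 14 days, so excluded events and excluded time leave together.

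**The case against.** The strongest case on the other side is that the SAP rule is defensible and nearly harmless. For completers it aligns events with person-time. The protocol does not: it counts events to Visit 13 (11.3.2) but divides by exposure (11.4.3.1.1), which stops one dose interval after the last dose (11.4.1.1). The study is descriptive and single-arm, and the shift in the primary percentage is a fraction of a point. SAEs and AEs leading to death are also tabulated regardless of treatment-emergent status (Protocol 11.4.3.1.2). The AESI endpoint is worded as over the study, although SAP 2.4.5.1 applies the TEAE methodology to it. All of this stands. It limits the size of the point but does not remove the undeclared difference.

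Three stronger readings might be inferred, and the documents do not support them:
- **That everything found at a late Visit 13 is lost.** SAP 2.4.5 classifies by onset. An AE that began inside the window and is first reported at Visit 13 counts, and SAP 2.5.2 treats incomplete onset dates as treatment-emergent unless they show otherwise. A pregnancy is left out only if it is dated after the window closes.
- **That any late visit opens a gap.** The window moves with the actual last dose, so a late dose can absorb a late visit.
- **That the completer event rate is biased downward by mismatch.** Step 7 shows that it is not.

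**Conclusion.** The point holds as an undeclared difference in the definition of the primary endpoint, with a small numerical effect. For patients who reach Week 144 without a dose at Visit 13, AEs with onset after last dose + 14 days and up to Visit 13 are TEAEs under the protocol and not under the SAP. This lowers counts and percentages; with a 7-day gap, the percentage with any TEAE falls by at most about 0.24 points at 50 to 200 per 100 person-years. The relative effect is larger for AEs dated to a scheduled test, about 4% under the assumptions of step 6.

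The size rests on assumed AE rates, a constant hazard and an assumed ±7-day window for Visit 13; the 47% and 4% figures also need independent uniform offsets. The Day 1008 result depends on there being no dose at Visit 13, on which the protocol contradicts itself. It does not extend to patients who stop at market availability before Week 144: the SAP does not say whether they are completers, and the spacing of their last dose and final visit is not stated.

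**What to change.** 1. In SAP 2.3.2 and 2.4.5, end the completers' treatment-emergent period at the later of Visit 13 and last dose + 14 days.
2. In SAP 2.4.5.1, end their person-time for the event rate on the same date. Leave the exposure-duration summary in SAP 2.4.3.1 unchanged.
3. In SAP 1.5, declare that this person-time departs from the protocol's exposure-based denominator, and declare the 12-week window for premature discontinuers.
4. In SAP 2.4.5.1, align the sentence that counts all events reported in the follow-up period with the TEAE numerator.
5. Reconcile Protocol 10.3.4 with the flow chart on whether Visit 13 is a dosing day. Which is right is for the sponsor to settle.

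The cost is SAP wording and one derived date, plus the reconciliation of the protocol text. The downside is that a few off-drug days enter both numerator and denominator for completers.

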2.4 STATISTICAL METHODS

2.4.1 Demographics and baseline characteristics

Parameters will be summarized on the enrolled population.

Continuous data will be summarized using the number of available data (n), mean, standard deviation (SD), median, minimum, and maximum. Categorical and ordinal data will be summarized using the number and percentage of patients.

Parameters described in [Section 2.1.1](#) will be summarized for the safety population using descriptive statistics.

Relevant medical or surgical history is collected on CRFs and will be summarized. The alcohol habits, smoking history, and pregnancy test data at baseline will also be summarized.

2.4.2 Concomitant medications

A concomitant medication is any treatment received by the patient concomitantly to the IMP. Concomitant medications will be presented for the safety population.

Medications will be summarized according to the WHO-DD dictionary, considering the first digit of the anatomic category (ATC) class (anatomic category) and the first 3 digits of the ATC class (therapeutic category). All ATC codes corresponding to a medication will be summarized, and patients will be counted once in each ATC category (anatomic or therapeutic) linked to the medication. Therefore patients may be counted more than once for the same medication if it was prescribed for different indications.

The tables for concomitant medications will be sorted by decreasing frequency of ATC followed by all other therapeutic classes based on overall incidence. In case of equal frequency regarding ATCs (anatomic or therapeutic categories), alphabetical order will be used.

2.4.3 Extent of investigational medicinal product exposure and compliance

The extent of IMP exposure and compliance will be assessed and summarized within the safety population ([Section 2.3.2](#)).

2.4.3.1 Extent of investigational medicinal product exposure

The extent of IMP exposure will be assessed by the duration of IMP exposure.

Duration of exposure to IMP is defined as: last dose date – first dose date of dupilumab + 14, regardless of unplanned intermittent discontinuations. Duration of exposure will be

Statistical Analysis Plan
LPS15023 - Dupilumab
summarized using descriptive statistics such as mean, standard deviation (SD), median, minimum, and maximum.

15-Mar-2021
Version number: 2.0

Duration of IMP exposure will be summarized descriptively as a quantitative variable (number, mean, SD, median, minimum, and maximum). In addition, duration of treatment exposure will also be summarized categorically by numbers and percentages for each of the following categories and cumulatively according to these categories in days: >0-4, >4-12, >12-24, >24-48, >48-72, >72-96, >96-120, >120-142, >142.

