8.1.3 Dose schedule

The IMP will be administered every 14±3 days (q2w). The consecutive doses of the IMP must be separated by ≥11 days to avoid an overdose. If in TRAVERSE the patient was already self-injecting, and/or parent/caregiver(s) was already injecting the patient, the Investigator or delegate will supervise the injection, or the Investigator or delegate will train the patient (and/or parent/caregiver[s]) on how to prepare and inject IMP at Start-of-treatment Visit (Visit 1) and will inject the first injection. For patients who discontinued treatment for ≥6 weeks after TRAVERSE ie, patients requiring a loading dose, the first injection is the first of the 2 injections of IMP (for the 600 mg dose).

Reminder: patients will be monitored for any signs or symptoms of hypersensitivity reactions for a minimum of 30 minutes after IMP injection on-site visit days. For patients who experience hypersensitivity reactions upon retreatment, ie, at the Start-of-treatment Visit (Visit 1), or for patients with long off-treatment interval after the completion of TRAVERSE, additional on-site IMP administration visits may be scheduled at the Investigator's discretion.

Subcutaneous injection sites should be alternated between the 4 quadrants of the abdomen (avoiding navel and waist areas), the upper thighs, or upper arms (lateral side), so that the same site is not injected twice consecutively. Injection in the upper arms could be done only by a trained person (parent/caregiver[s] trained by the Investigator or delegate) or health care professional but not the patient themselves. This instruction pertains to the day of the loading dose as well as for subsequent q2w injections. For each injection, the anatomic site of administration will be recorded in the electronic case report form (eCRF) and in the home-dosing diary.

Detailed instructions for transport, storage, and administration of IMP will be provided to the patient, and Investigators should ensure that these instructions are followed. Patients will complete a home-dosing diary to document compliance with self-injection (or parent/caregiver injection) of IMP.

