1 OVERVIEW AND INVESTIGATIONAL PLAN

1.1 STUDY DESIGN AND RANDOMIZATION

The LPS15023 study is a Phase IIIb, non-randomized, open-label, interventional, outpatient, prospective, multinational, multicenter, noncomparative, single-arm, safety study in patients with moderate to severe asthma who completed the parent study, TRAVERSE-LTS12551, from here on referred to as TRAVERSE.

This study will evaluate the long-term safety of dupilumab 300 mg q2w administered subcutaneously (SC) over a maximum of 144 weeks.

It is expected that approximately 750 patients will enroll in this study.

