1.4 STUDY PLAN

The LPS15023 study consists of 3 periods:

- Start-of-treatment Visit (Visit 1): After completing the EOT Visit (Visit 17) in TRAVERSE, eligible patients should rollover into LPS15023.
- Treatment period (Visit 2 to Visit 12): Open-label treatment for up to 144 weeks (Visit 13, approximately 3 years).
- End-of-treatment/End-of-study (Visit 13).

Patients who prematurely and/or permanently discontinue treatment will be scheduled for the EOT Visit, and the EOS Visit will be scheduled for 12 weeks later for follow-up on AEs.

Statistical Analysis Plan
LPS15023 - Dupilumab

15-Mar-2021
Version number: 2.0

After completing the treatment period in TRAVERSE, eligible patients who have signed the informed consent form (ICF) should perform the assessments of the Start-of-treatment Visit (Visit 1). Patients will receive treatment until dupilumab approval for use in asthma and market availability to patients, or for a maximum of 144 weeks (i.e. about 3 years) after the Start of treatment (Visit 1), whichever comes first.

The end of clinical trial is defined as the “last patient last visit” planned in the protocol, i.e. the EOT/EOS Visit (Visit 13). The Sponsor reserves the right to discontinue the study at any time.

Study Flow Chart (copied from [section 1.1](#) of protocol)

Study periods	Start-of-Treatment	Treatment Period (144 weeks)	End-of-Treatment / End-of-Study
Week (W)	W0	W12-W132 (Visit every 12 weeks)	W144
VISIT	V1 ^a	V2-V12 ^b	V13 ^c
Enrollment			
Informed consent	X		
Patient demography	X		
Eligibility criteria	X		
Treatment			
Contact IRT	X	X	X
IMP dispensation/administration ^d	X	X	
IMP accountability	X	X	X
Injection training/technique observation ^e	X	X	
Dispense home-dosing diary ^f	X	X	
Safety			
Clinical laboratory ^g	X ^h	X	X
Adverse event reporting	X	X	X
Symptom-driven physical examination and vital signs	X	X	X
Concomitant medications	X	X	X

AE = adverse events; eCRF = electronic case report form; EOS = end-of-study; EOT = end-of-treatment; IMP = investigational medicinal product; IRT = interactive response technology; q2w = every 2 weeks; V = (study) visit; W = (study) week; WOCBP = women of child-bearing potential.

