2.4.5.1 Analyses of adverse events

Analysis of Primary Safety Endpoint

Incidence rates of TEAEs with corresponding 95% CI (by the Clopper-Pearson method) will be calculated as follows:

- Incidence Rate (IR) = number patients with one or more TEAEs / number of subjects at risk (i.e. safety population) × 100

Event rates per 100 person-years of TEAEs with corresponding 95% CI (two-sided exact Poisson CIs) will be calculated. All events reported during the study follow-up period will be counted, regardless of whether they are reported in the same subject (i.e., multiple events per subjects), or different subjects. The person-years at follow-up will be calculated using the standard on-treatment duration formula: (the date of last IMP – date of first dose of IMP + 14 days)/365.25. Note that date of first dose of IMP, is in regards to first dose of this study, not first dose of the parent study. Event rate per person-years will be calculated as follows:

- Event rate (ER) = number of TEAEs / number of person-years at follow up

Analysis of Secondary Safety Endpoints

Incidence rates with corresponding 95% CI (Clopper-Pearson method) and event rates with corresponding 95% CI (exact Poisson method) will be presented for AESIs, described in [section 2.1.4.1](#), using the same methodology described above.

Incidence rates with corresponding 95% CI (Clopper-Pearson method) will be presented for SAEs/death over the study.

Incidence rates with corresponding 95% CI (Clopper-Pearson method) will be presented for AEs leading to study discontinuation over the study.

Generalities

The primary focus of adverse event reporting will be on treatment-emergent adverse events.

Statistical Analysis Plan
LPS15023 - Dupilumab

15-Mar-2021
Version number: 2.0

If an adverse event date/time of onset (occurrence, worsening, or becoming serious) is incomplete, an imputation algorithm will be used to classify the adverse event as pretreatment, treatment-emergent, or posttreatment. The algorithm for imputing date/time of onset will be conservative and will classify an adverse event as treatment emergent unless there is definitive information to determine it is pretreatment or posttreatment. Details on classification of adverse events with missing or partial onset dates are provided in [Section 2.5.3](#).

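### The exposure-duration categories are in days but fit only weeks: two of nine bins can never hold a patient, and everyone treated beyond about 20 weeks falls in the open-ended top bin

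*SAP*

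**What the plan says.** SAP section 2.4.3.1 defines duration of exposure as "last dose date – first dose date of dupilumab + 14, regardless of unplanned intermittent discontinuations". It asks for the usual continuous summaries and then for counts and percentages by category, and "cumulatively according to these categories in days: >0-4, >4-12, >12-24, >24-48, >48-72, >72-96, >96-120, >120-142, >142".

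Other parts of the documents fix the scale of that variable:

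- SAP section 1.1 sets treatment "over a maximum of 144 weeks". The flow chart in SAP section 1.4 has visits every 12 weeks from week 12 to week 132 and a final visit at week 144. No study drug is dispensed at the final visit.
- SAP section 2.4.5.1 shows that the 14 in the duration formula is in days. Its person-years formula uses "date of first dose of IMP + 14 days)/365.25".
- SAP section 2.3.2 limits the safety population, on which exposure is summarised, to patients who received at least one full or partial dose.
- Protocol section 8.1.3 sets the dosing interval at 14 days, give or take 3.

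Protocol section 11.4.1.1 gives no exposure categories, so the SAP is the only source for them. The one modification listed in SAP section 1.6 concerns COVID-19 analyses and leaves the categories alone.

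**The concern.** The categories end at 142 on a variable that can reach 1008 in the stated unit, and they begin below the smallest value the formula can give. Both faults point to a wrong unit.

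The study has one objective, to describe long-term safety, and Protocol section 4.2 puts the emphasis on late-onset events. A reader will want to know how many patients contributed roughly one, two and nearly three years of treatment. The cumulative exposure table is the planned output that answers this. Durations may vary widely, because treatment ends at approval and market availability or at 144 weeks, whichever comes first. A mean, median and range do not give the number of patients who reached each milestone. Built literally, the table would put a patient treated for 5 months and one treated for 33 months in the same row.

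**Working it through.** **Inputs.** Maximum treatment of 144 weeks (SAP 1.1); duration = last dose date − first dose date + 14 days (SAP 2.4.3.1 and 2.4.5.1); dosing every 14 days, range 11 to 17 (Protocol 8.1.3); no dispensing at week 144 (SAP 1.4, flow chart note d); nine categories with upper limits 4, 12, 24, 48, 72, 96, 120 and 142, then an open top category (SAP 2.4.3.1).

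**1. Reproduce the stated maximum.** Dosing every two weeks from week 0 to week 142 gives 142/2 + 1 = 72 doses. The formula gives 71 × 14 + 14 = 1008 days, and 1008/7 = 144 weeks. This agrees with the SAP, so the duration formula is sound.

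**2. Upper end, read as days.**
- 142/7 = 20.3 weeks.
- (1008 − 142)/1008 = 85.9% of the possible range lies in the top category.
- Ten doses give 9 × 14 + 14 = 140 days, in the second-highest category. Eleven give 10 × 14 + 14 = 154 days, in the top one.
- At the extreme intervals, a patient enters the top category at dose 13 with 11-day gaps (12 × 11 + 14 = 146 days) or at dose 9 with 17-day gaps (8 × 17 + 14 = 150 days).
- Week 24 is day 168, so that visit and every later one lie in the top category.

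**3. Lower end, read as days.** One dose gives 0 + 14 = 14 days. This exceeds 12, so the first two categories cannot hold anyone, whatever the dosing interval. The missing-date rules in SAP section 2.5.2 do not change this. A missing last-dose date adds 11 days (one dose becomes 11 + 14 = 25 days). A missing first-dose date leaves the duration missing, so that patient enters no category. The other seven categories can be reached.

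**4. Place all 72 nominal durations in the categories.** After *k* doses the duration is 14*k* days, or 2*k* weeks, for *k* = 1 to 72.

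| Category | Durations, read as days | Durations, read as weeks |
|---|---|---|
| >0-4 | 0 | 2 |
| >4-12 | 0 | 4 |
| >12-24 | 1 | 6 |
| >24-48 | 2 | 12 |
| >48-72 | 2 | 12 |
| >72-96 | 1 | 12 |
| >96-120 | 2 | 12 |
| >120-142 | 2 | 11 |
| >142 | 62 | 1 |

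These are counts of possible durations, not of patients. In days, 62 of 72 share one row and two rows are empty. In weeks, no row is empty: a single dose (2 weeks) falls in the first and a full course (144 weeks) in the last.

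**5. Which unit was meant.** The cut-points 12, 24, 48, 72, 96 and 120 are all visit weeks. The value 142 is not a visit week, but it is the week of the last nominal dose, which follows from two-weekly dosing with none dispensed at week 144. The value 4 is not a visit week either and says nothing about the unit.

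**The case against.** The strongest reply is that little depends on these categories. The primary and secondary endpoints are incidence rates and event rates. Their denominators are the safety population and person-years, and neither uses the categories. The mean, SD, median, minimum and maximum of exposure are also reported, so a reader would still see whether typical exposure was nearer 5 or 33 months. The fault would be obvious as soon as the table was run, and it can be corrected from the same data. All of this stands. It limits the point to one table, with no bias and no effect on any endpoint.

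Three further cautions are also fair. The 85.9% is a share of the time axis, not of patients; the documents do not give the distribution of exposure. That weeks were intended is an inference, since no passage says so. Even in weeks, the cut-points only approximate whole years: 48 and 96 weeks are 336/365.25 = 0.92 and 672/365.25 = 1.84 years.

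None of this makes the categories usable as written. A programmer who follows the SAP produces an uninformative table, and one who silently corrects the unit produces an output that departs from the SAP without a record.

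**Conclusion.** The categories are wrong as written. In days, two of the nine are empty by construction, and every patient with more than 142 days (20.3 weeks) of exposure shares one open-ended row covering 85.9% of the possible range. This rests only on the SAP's own formula, its 144-week maximum and the requirement of at least one dose. It holds for any dosing interval the protocol allows. The count of 62 out of 72 durations additionally assumes regular 14-day dosing.

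Weeks is almost certainly the intended unit, because the cut-points follow the study calendar and every category then becomes usable. The consequence is a categorical and cumulative exposure table that cannot show how many patients had long treatment. The continuous exposure summaries, incidence rates and event rates are unaffected.

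**What to change.** In SAP section 2.4.3.1, have the sponsor confirm the unit and state the categories in weeks, keeping the cut-points. Define weeks of exposure as (last dose date − first dose date + 14)/7, and record the change in SAP section 1.6 before the table is produced. The cost is one word in the SAP and one division in the program, with no new data.

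Optionally, add a line with total patient-years to the exposure table. That quantity already has to be computed for the event rates. The correction does not depend on it.
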